2.3. Exploratory PK variables

Emodepside plasma concentration–time data will be used to derive the following PK parameters of emodepside:

- After a single dose of emodepside (Day 0):
 - Cohorts 1 & 2: $AUC_{24,norm}$, $C_{max,norm}$, t_{max} , MRT_{last} , V_z/F
 - Cohorts 3: $AUC_{12,norm}$, $C_{max,norm}$, t_{max} , MRT_{last} , V_z/F
- After multiple doses of emodepside (Day 9):
 - $AUC_{\infty,norm}$, $AUC_{12,norm}$, $AUC_{24,norm}$, AUC_{last} , AUC_{last}/D , $AUC_{last,norm}$, $C_{max,ss,norm}$, $t_{1/2}$, λ_z , t_{max} , MRT_{∞} , V_z/F , CL_{ss}/F
 - Other optional parameters: AUC_{t-inf} , $\%AUC_{extra}$, points terminal

3. Study design and study design rationale

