7.1. Doses and treatment regimens

Randomised subjects will be given a unique ID (subject number; Table 6) that will be recorded in the case report form (CRF), and will be retained throughout the study.

This subject number will also appear on the study medication containers.

Table 6 . Study treatment: Subject numbers, Formulation, and Dose-Levels by Cohort

	Subject numbers ^a	Formulation and route of administration	Planned subjects	
			Emodepside	Matching placebo
Cohort 1	1001 – 1008	5 mg LSF solution OD, or placebo, by mouth	6	2
Cohort 2	2001 – 2008	10 mg LSF solution OD, or placebo, by mouth	6	2
Cohort 3	3001 – 3008	10 mg LSF solution BID, or placebo, by mouth	6	2

^a Any subjects who are replaced in a cohort will have the subject number incremented by 100 (eg, 1001 would be replaced by 1101)

Subjects will receive the study medication according to fasting instructions given in Section 4.3: On dosing days, following an 9 h overnight fast (no food or drink, except water), Investigator site personnel will administer study medication (active or placebo) to subjects with 240 mL ambient temperature water.

Subjects in Cohort 3 will be given an evening dose approximately 12 h after their morning dose on Days 0–9: they'll fast for 2 h before and 1 h after that evening dose.

Study treatment will be administered under the supervision of Investigator site personnel, following site standard procedures to ensure treatment compliance.

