8.4.2. PK assessments

Blood samples assaying the concentration of emodepside and its metabolites in plasma will be collected at the time points indicated in the Schedule of events (Section 5). The exact date and time of PK blood sampling will be recorded in the CRF.

Blood samples for PK purpose will be taken from either arm. Samples will be collected either by cannulation or by venepuncture. After processing, samples will be frozen and transported on dry ice to the Bioanalysis Laboratory. Detailed instructions for collection, processing, storage, and transport of samples will be provided in the Study Procedures Manual. Blood volumes for PK samples are shown in Section 8.4.4.

Plasma will be analysed for emodepside using a validated assay method. Full details of the method will be presented in a separate document and all the results will be reported in the bioanalytical report at the end of the study. On Profile Days (Day 0 and Day 9), frequent blood samples will be collected for PK estimation and emodepside plasma concentrations. On each treatment period, the following PK parameters of emodepside will be derived for each subject:

Single Dose Day 0 parameters

AUC ₁₂	The area under the concentration-time curve from time zero (pre-dose) to 12 h will be calculated using a trapezoidal method.
AUC ₂₄	The area under the concentration-time curve from time zero (pre-dose) to 24h will be calculated using a trapezoidal method.
AUC _{12/D}	The area under the concentration-time curve from time zero (pre-dose) to 12 h, corrected for dose
AUC _{24/D}	The area under the concentration-time curve from time zero (pre-dose) to 24h, corrected for dose
AUC _{12,norm}	The area under the concentration-time curve from time zero (pre-dose) to 12 h corrected by dose and body weight
AUC _{24,norm}	The area under the concentration-time curve from time zero (pre-dose) to 24h corrected by dose and body weight
C _{max}	The observed maximum plasma concentration measured in a subject after dosing identified by inspection of the drug concentration vs. time data.
C _{max/D}	The observed maximum plasma concentration measured in a subject after dosing identified by inspection of the drug concentration vs. time data, corrected for dose.
C _{max,norm}	The observed maximum plasma concentration corrected by dose and body weight
t _{max}	The time at which C _{max} was apparent, identified by inspection of the drug concentration vs. time data.

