18 ATTACHMENTS

18.1 Table of Contents for Data Display Specifications

For overall page layout refer to Appendix C.

Tables, figures and listings will be labelled A (for Cohorts 1 and 2) and B (for Cohort 3), e.g. 14.1A, 14.1B. Separate tables will be produced for Cohorts 1 and 2 and for Cohort 3.

The numbering in the tables below will take precedence over the numbering in the shells.

The following tables and figures will be produced (templates provided in Section 18.2.1):

Table	Description	Population	Source Listing	Template (Shells below)
10.1	Summary of subject disposition	Safety	16.2.1.2, 16.2.3.1	T_SD1
14.1	DEMOGRAPHIC DATA			
14.1	Summary of demographic characteristics	Safety	16.2.4.1	T_DM1
14.2	PHARMACOKINETIC AND PHARMACODYNAMIC DATA			
14.2.1.1	Summary of emodepside plasma pharmacokinetic concentration-time data [units]	PK Concentration	16.2.6.1.1	T_PK1
14.2.1.2	Summary of derived emodepside plasma pharmacokinetic parameters	PK Parameter	16.2.6.1.2	T_PK3
14.2.1.3	Summary of log-transformed derived emodepside plasma pharmacokinetic parameter	PK Parameter	16.2.6.1.2	T_PK4
14.2.2.1	Summary of glucose	Safety	16.2.6.2.1	T_LB2
14.2.2.2	Summary of insulin	Safety	16.2.6.2.1	T_LB2
14.2.2.3	Summary of glucagon	Safety	16.2.6.2.1	T_LB2
14.2.2.4	Summary of cortisol	Safety	16.2.6.2.1	T_LB2
14.2.3.1	Summary of oral glucose tolerance test results	Safety	16.2.6.2.1	T_LB2
14.3	SAFETY DATA			
14.3.1.1	Summary of treatment-emergent adverse events	Safety	16.2.7.1	T_AE1
14.3.1.2	Summary of drug-related treatment-emergent adverse events	Safety	16.2.7.1	T_AE1
14.3.1.3	Summary of treatment-emergent adverse events by severity	Safety	16.2.7.1	T_AE3
14.3.2.1	Listing of fatal adverse events	Safety	16.2.7.1	L_AE1_PG
14.3.2.2	Listing of non-fatal serious adverse events	Safety	16.2.7.1	L_AE1_PG
14.3.2.3	Listing of other significant adverse events	Safety	16.2.7.1	L_AE1_PG
14.3.3	Narratives of deaths, other serious and significant adverse events	Safety		-
14.3.4	Summary of laboratory values of potential clinical importance	Safety	16.2.8.1, 16.2.8.3	T_LB1
14.3.5.1	Summary of chemistry laboratory values	Safety	16.4	T_LB2
14.3.5.2	Summary of haematology laboratory values	Safety	16.4	T_LB2
14.3.5.3	Summary of coagulation laboratory values	Safety	16.4	T_LB2
14.3.5.4	Summary of urinalysis results	Safety	16.2.8.5	T_UR1

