AUC ₂₄ /Dose **	Dose-normalised AUC from time zero to 24 h	The dose-normalised AUC from time zero to 24h will be calculated as AUC ₂₄ /Dose Administered	(h*ng/mL)/mg	Y	-	AUCINTD	AUC ₂₄ /D
AUC _{24, norm} **	Area under the concentration-time curve from time zero to 24h corrected by dose and body weight	The AUC from time zero to 24h normalised by dose and body weight will be calculated as AUC ₂₄ /(Dose administered*body weight)	(h*ng/mL)/(mg*kg)	Y	-	AUCINTWD	AUC _{24, norm}
Clearance, volume of distribution and mean residence time							
V _z /F	Apparent volume of distribution during terminal phase after non-intravenous administration	Apparent volume of distribution will be calculated using the following formula: $V_z / F = \frac{Dose}{\lambda_z \cdot AUC_{\infty}}$	L	Y	V _z _pred (actually derives V _z _F_pred for oral dose)	VZFP	V _z /F
MRT _{last}	Mean Residence Time	The mean residence time will be calculated using: $MRT = \frac{AUMC}{AUC_{\infty}}$	h	Y	MRTLST_pred	MRTEVLST	MRT _{last}

* Calculated only for Cohort 3

**Calculated only for Cohorts 1 and 2

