3.1.2 Multiple Dose

Emodepside parameters to be calculated on Day 9.

Text Symbol	Definition	Calculation	Typical Units	Log Transform	WNL	CDISC Controlled Terminology	TFL Symbol
Concentrations during and after multiple dosing							
C_{trough}	Trough plasma concentration	Trough plasma concentration (measured concentration at the end of a dosing interval at steady state [taken directly before next administration]) obtained directly from the concentration-time data.	ng/mL	Y	-	CTROUGH	C_{trough}
Concentrations and times (after final dose)							
$C_{\text{max,ss}}$	Maximum (peak) plasma concentration at steady state	The maximum (peak) plasma concentration will be obtained directly from the concentration-time data.	ng/mL	Y	Cmax	CMAX	$C_{\text{max,ss}}$
$C_{\text{max,ss}}/\text{Dose}$	Dose-normalised C_{max} at steady state	The dose-normalised C_{max} will be calculated as $C_{\text{max}}/\text{Dose}$ administered	(ng/mL)/mg	Y	Cmax_D	CMAXD	$C_{\text{max,ss}}/D$
$C_{\text{max,ss,norm}}$	Observed maximum plasma concentration corrected by dose and body weight at steady state	The C_{max} normalised by dose and body weight will be calculated as $C_{\text{max}}/(\text{Dose administered} * \text{body weight})$	(ng/mL)/(mg*kg)	Y	-	CMAXWD	$C_{\text{max,ss,norm}}$
t_{max}	Time to reach maximum (peak) plasma concentration	The first time of maximum (peak) plasma concentration will be obtained directly from the concentration-time data.	h	N	Tmax	TMAX	t_{max}
Half-life (after final dose)							
λ_z	Terminal rate constant	The apparent terminal phase rate-constant (λ_z) will be estimated by linear regression of logarithmically transformed concentration versus time data.	1/h	Y	Lambda_z	LAMZ	λ_z
$t_{1/2}$	Terminal half-life	The terminal half-life calculated from the terminal slope of the log concentration-time curve, as follows: $t_{1/2} = \frac{\log_e 2}{\lambda_z}$	h	Y	HL_Lambda_z	LAMZHL	$t_{1/2}$
$t_{1/2,\text{dom}}$	Dominant half-life	The dominant half-life calculated from the terminal slope of the log concentration-time (0-24h) curve, as follows:	h	Y	HL_Lambda_z	LAMZHLD	$t_{1/2,0-24}$

Text Symbol	Definition	Calculation	Typical Units	Log Transform	WNL	CDISC Controlled Terminology	TFL Symbol
		$t_{1/2, dom} = \frac{\log_e 2}{\lambda_z}$					
Areas under the curve (after final dose)							

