AUC _{last}	Area under the plasma concentration-time curve from time zero to time of last measurable concentration	The area under the concentration-time curve from zero time (pre-dose) to the time of last quantifiable concentration will be calculated using the (specified) trapezoidal method.	h*ng/mL	Y	AUClast	AUCLST	AUC _{last}
AUC _{last} /Dose	Dose-normalised AUC from time zero to last measurable concentration	The dose-normalised AUC from time zero to last measurable concentration will be calculated as AUC _{last} /Dose Administered	(h*ng/mL)/mg	Y	-	AUCLSTD	AUC _{last} /D
AUC _{last,norm}	Area under the concentration-time curve from time zero to time of last measurable concentration corrected by dose and body weight	The AUC from time zero to last measurable concentration normalised by dose and body weight will be calculated as AUC _{last} /(Dose administered*body weight)	(h*ng/mL)/(mg*kg)	Y	-	AUCLSTWD	AUC _{last,norm}
AUC ₁₂ *	Area under the plasma concentration-time curve from time zero to time 12 h	The area under the concentration-time curve from zero time (pre-dose) to time 12 h will be calculated using the (specified) trapezoidal method. If λ_z is not estimable, a partial AUC is not calculated (when $t_{last} < t$).	h*ng/mL	Y	User specified area	AUCINT	AUC ₁₂
AUC ₁₂ /Dose *	Dose-normalised AUC from time zero to 12 h	The dose-normalised AUC from time zero to 12h will be calculated as AUC ₁₂ /Dose Administered	(h*ng/mL)/mg	Y	-	AUCINTD	AUC ₁₂ /D
AUC _{12,norm} *	Area under the concentration-time curve from time zero to 12h corrected by dose and body weight	The AUC from time zero to 12h normalised by dose and body weight will be calculated as AUC ₁₂ /(Dose administered*body weight)	(h*ng/mL)/(mg*kg)	Y	-	AUCINTWD	AUC _{12,norm}

Text Symbol	Definition	Calculation	Typical Units	Log Transform	WNL	CDISC Controlled Terminology	TFL Symbol
AUC ₂₄ **	Area under the plasma concentration-time curve from time zero to time 24 h	The area under the concentration-time curve from zero time (pre-dose) to time 24 h will be calculated using the (specified) trapezoidal method. If λ_2 is not estimable, a partial AUC is not calculated (when $t_{last} < t$).	h*ng/mL	Y	User specified area	AUCINT	AUC ₂₄
AUC ₂₄ /Dose **	Dose-normalised AUC from time zero to 24 h	The dose-normalised AUC from time zero to 24h will be calculated as AUC ₂₄ /Dose Administered	(h*ng/mL)/mg	Y	-	AUCINTD	AUC ₂₄ /D

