AUC _{24, norm} **	Area under the concentration-time curve from time zero to 24h corrected by dose and body weight	The AUC from time zero to 24h normalised by dose and body weight will be calculated as AUC ₂₄ /(Dose administered*body weight)	(h*ng/mL)/(mg*kg)	Y	-	AUCINTWD	AUC _{24, norm}

Text Symbol	Definition	Calculation	Typical Units	Log Transform	WNL	CDISC Controlled Terminology	TFL Symbol
AUC _∞	Area under the plasma concentration-time curve from time zero to infinity	The area under the concentration-time curve will be calculated using the (specified) trapezoidal method for the interval 0 to t _{last} (time t _{last} is the time at which the last non-zero level was recorded), plus the area under the exponential curve from t _{last} to infinity, calculated as follows: $AUC_{t-\infty} = \frac{\hat{C}_t}{\lambda_z}$ where \hat{C}_t is the predicted value of the concentration at t _{last} .	h*ng/mL	Y	AUCINF_pred	AUCIFP	AUC _{inf}
AUC _∞ /Dose	Dose-normalised AUC from time zero to infinity	The dose-normalised AUC from time zero to infinity will be calculated as AUC _∞ /Dose Administered	(h*ng/mL)/mg	Y	-	AUCIFPD	AUC _∞ /D
AUC _{∞,norm}	Area under the concentration-time curve from time zero to infinity corrected by dose and body weight	The AUC from time zero to infinity normalised by dose and body weight will be calculated as AUC _∞ /(Dose administered*body weight)	(h*ng/mL)/(mg*kg)	Y	-	AUCIFPWD	AUC _{∞,norm}
%AUC _{extrap}	Percentage of AUC _∞ extrapolated from from t _{last} to infinity	$\% AUC_{extrap} = \frac{100 \times AUC_{t-x}}{AUC_x}$	%	N	AUC_%EXTRAP_pred	AUCPEP	%AUC _{extrap}
Clearance, volume of distribution and mean residence time (after final dose)							
CL _{SS} /F	Apparent total clearance from plasma after oral administration	Apparent total clearance from plasma will be calculated using the following formula: $CL_{SS} / F = \frac{Dose}{AUC_t}$	L/h	Y	Clss_pred (actually derives Clss_F_pred for oral dose)	CLFTAU	CL _{SS} /F
V _z /F	Apparent volume of distribution after non-intravenous administration calculated at steady state	Apparent volume of distribution calculated at steady state will be calculated using the following formula: $V_z / F = \frac{Dose}{\lambda_z \cdot AUC_t}$	L	Y	Vz_pred (actually derives Vz_F_pred for oral dose)	VZFTAU	V _z /F

Text Symbol	Definition	Calculation	Typical Units	Log Transform	WNL	CDISC Controlled Terminology	TFL Symbol

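### The SAP's eight weight-normalised PK parameters divide by body weight as well as dose, which adds a weight effect instead of removing one

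*SAP*

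**What the plan says.** Protocol section 8.4.2 describes the normalised parameters in words only. Cmax,norm, for instance, is "The observed maximum plasma concentration corrected by dose and body weight". No formula is given there.

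SAP Appendix B supplies the formula. In sections 3.1.1 and 3.1.2 the divisor is ("Dose administered*body weight") in every normalised row:

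- **Day 0 (three rows):** Cmax, AUC12, AUC24.
- **Day 9 (five rows):** Cmax,ss, AUClast, AUC12, AUC24, AUC∞.

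The definition column states the purpose, for example "Observed maximum plasma concentration corrected by dose and body weight at steady state". The calculation column repeats the intention before giving the product formula: "The AUC from time zero to last measurable concentration normalised by dose and body weight will be calculated as" for AUClast and "The AUC from time zero to infinity normalised by dose and body weight will be calculated as" for AUC∞. The units column has (mg*kg) in the denominator in all eight rows.

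Doses are fixed amounts. Cohort 1, for example, receives "5 mg LSF solution OD, or placebo, by mouth" (protocol section 7.1). Protocol section 2.3 places the normalised parameters under "Exploratory PK variables", and SAP section 4.2.2 does the same. All eight are marked for log transformation, so they go into SAP Table 14.2.1.3, "Summary of log-transformed derived emodepside plasma pharmacokinetic parameter".

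**The concern.** A weight correction should take out the part of the between-subject difference that comes from body size. At the same mg dose a heavier subject receives fewer mg/kg, and exposure would be expected to be lower or, at most, unchanged. To put subjects on a common mg/kg footing, exposure has to be divided by dose per kg, which means multiplying by weight. The SAP divides by weight, so it moves the value in the wrong direction.

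The geometric means and %CV of these parameters will be reported as dose- and weight-normalised, next to dose-only parameters that depend less on weight. A reader could take the larger spread as a property of the drug. Comparisons across cohorts are affected too. The geometric mean of X/(D × W) equals the geometric mean of X/D divided by the geometric mean weight. With six active subjects per cohort, any chance difference in weight between cohorts therefore enters the dose comparison directly.

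**Working it through.** The plan states no figure to reproduce, so the check is algebraic, with illustrative sizes.

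**Inputs from the documents**

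- Formula and units: SAP Appendix B 3.1.1 and 3.1.2. The row count is 3 + 5 = 8.
- Fixed mg dosing: protocol section 7.1.
- BMI 18.0 to 30.1 kg/m²: protocol section 4.1. At one height this is a weight ratio of 30.1/18 = 1.67.

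**Assumptions not in the documents**

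- Exposure at a fixed dose varies as weight^(−b), with b from 0 to 1.
- Residual log-SD is 0.25. Weight log-SD is sw = 0.15, varied to 0.10 and 0.20.

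**Step 1: slope of log parameter on log weight**

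| Form | Proportional to | Slope k |
|---|---|---|
| Dose-only, X/D | W^(−b) | −b |
| SAP, X/(D × W) | W^(−(b+1)) | −(b+1) |
| Per-kg, X/(D/W) = X × W/D | W^(1−b) | 1−b |

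Whatever b is, the SAP form shifts the dose-only slope by −1. It is flat only at b = −1, that is, if exposure rose in proportion to weight. It doubles the log-scale slope exactly at b = 1.

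**Step 2: a single example**

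Take b = 1, dose 10 mg and a hypothetical AUC of 1000 at 70 kg. At 60, 70 and 90 kg the AUC is 1166.7, 1000 and 777.8.

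- SAP form: 1166.7/(10 × 60) = 1.94, 1000/(10 × 70) = 1.43, 777.8/(10 × 90) = 0.86.
- Per-kg form: 1166.7 × 60/10 = 7000, and 7000 at the other two weights as well.

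**Step 3: lightest against heaviest at one height (weight ratio 1.67)**

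| b | Dose-only, 1.67^b | SAP, 1.67^(b+1) |
|---|---|---|
| 0 | 1.00 | 1.67 |
| 0.5 | 1.29 | 2.16 |
| 1 | 1.67 | 2.80 |

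**Step 4: between-subject CV**

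The standard log-normal formula is CV = 100 × √(exp(k²sw² + 0.25²) − 1). For the SAP form at b = 1, k² = 4, so CV = 100 × √(exp(4 × 0.0225 + 0.0625) − 1) = 100 × √(exp(0.1525) − 1) = 40.6%. With sw = 0.15:

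| b | Per-kg | Dose-only | SAP |
|---|---|---|---|
| 0 | 29.8% | 25.4% | 29.8% |
| 0.5 | 26.6% | 26.6% | 34.6% |
| 0.75 | 25.7% | 27.9% | 37.5% |
| 1 | 25.4% | 29.8% | 40.6% |

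Over b = 0 to 1 the SAP form gives 27.4% to 32.9% with sw = 0.10 and 32.9% to 49.9% with sw = 0.20. Dose-only gives 25.4% to 27.4% and 25.4% to 32.9%. The SAP form is the more variable of the two in every case.

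**Step 5: difference in scale**

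Per-kg divided by SAP is (X × W/D) ÷ (X/(D × W)) = W². At an assumed height of 1.75 m the BMI limits are 18 × 3.0625 = 55.1 kg and 30.1 × 3.0625 = 92.2 kg. The factor therefore runs from about 3,040 to about 8,500. It differs between subjects, so relabelling the units would not repair the values.

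**The case against.** **Consequence.** The parameters are exploratory, and no test, model or decision uses them. Escalation uses unnormalised Cmax. The values are deterministic transforms, so the per-kg version can be recovered by multiplying by weight squared. All of this is true and limits the severity. It does not make the definition right, and a reader of a summary table cannot undo it.

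**Disclosure.** The tables will print the parameter symbol and its units, and (mg*kg) reveals the operation. That is a partial answer. The description still calls the operation a correction, and a reader has to notice an unusual unit to learn otherwise.

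**Remedy.** The per-kg form is less variable than dose-only only when b exceeds 0.5, and at b = 0 its CV equals that of the SAP form. This stands. The case for the per-kg form is that formula, units and description would agree. It also matches the non-clinical PK summary in protocol section 1.3, which reports clearance as L/(kg·h) and doses as mg/kg. It does not rest on a promised gain in precision.

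**Figures.** The CVs depend on assumed inputs. The 1.67-fold range holds at one height only. Eligibility does not restrict height, so the range across all eligible subjects can be wider. The %CV formula printed in SAP section 15 squares exp(SD), not SD, so it would give different percentages if applied literally. None of this changes the −1 shift in slope.

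**Conclusion.** The concern holds. Formula and units agree in all eight rows, so this is a consistent definition and not a single slip, and it would be programmed as written. The shift of −1 in the weight slope is exact. The statement that this worsens the weight dependence needs only b ≥ 0, and nothing in the documents suggests that exposure rises with weight. Under the assumptions stated, the SAP form raises between-subject CV over dose-only by 4.4 percentage points at b = 0 (29.8 − 25.4) and by 10.8 at b = 1 (40.6 − 29.8).

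This should be fixed before the derivations are run, but it is not critical. AUC, AUC/D, Cmax, Cmax/D, the accumulation ratios and the PK stopping rule are unaffected.

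**What to change.** In SAP Appendix B 3.1.1 and 3.1.2, redefine all eight normalised rows as parameter/(dose administered/body weight), equivalently parameter × body weight/dose administered. Change the units to (ng/mL)/(mg/kg) for Cmax and Cmax,ss, and to (h*ng/mL)/(mg/kg) for the AUCs. Keep the dose-only parameters, because the documents give no weight–exposure relation and the per-kg form need not be less variable.

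State in the same edit which weight is used. Protocol section 8.5.3 has it measured at screening and again on Day −1, and the SAP does not choose between them.

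The cost is wording in eight table rows and the matching derivation code. The values in Tables 14.2.1.2 and 14.2.1.3 and in Listing 16.2.6.1.2 change. No new data are needed.

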receiving placebo reported dry eye (n=1). All eye disorders AEs were of mild to moderate intensity, resolved spontaneously (without treatment), and were more frequently reported with highest dose (40 mg). Among them, the AEs of blurred vision, photophobia (“Increased ocular light sensitivity”), visual impairment (“distorted contrast perception”, “distorted colour perception”) reported by 8 out of 47 subjects receiving emodepside were considered as treatment-related by the Investigator. Also of note, at the highest dose (40 mg), lightheadedness (n=1), dizziness (n=1) or headache (n=1) were reported concomitantly to blurred vision.

None of the volunteers met any of the protocol-specified withdrawal criteria and overall tolerability to emodepside has been acceptable up to 20 mg. The presence of post-dose visual disturbances in subjects of Cohort 8 receiving either 40 mg solution or placebo may warrant some concern and escalation was stopped at this dose level.

The pharmacokinetic results obtained so far show that T_{max} for the LSF solution is consistently about 1 h post-dose when fasted. Mean C_{max} and AUC for the LSF solution have been roughly dose-proportional, with low to moderate inter-individual variability. The plasma half-life during the first 24 h is very short for a single dose of emodepside. After 3, 7, 16 and 47 h the maximum plasma concentration is reduced to 50%, 25%, 12.5% and 6.25% respectively. Terminal plasma half-life is 523 h. Although data of Cohort 9 (which was treated with a single dose of emodepside with food) are still under review, administration of the LSF of 10 mg with a high fat, high-calorie meal resulted in a clinically relevant food effect with a reduction of AUC to ~67%, C_{max} to 42% and a delay of the T_{max} up to 2.33 h. Therefore, the recommendation of administration of the emodepside (LSF) under fasted conditions is given.

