4.3 Statistical Hypotheses

Except for the analysis of pharmacokinetic data, no formal statistical testing will be done.

5 Study Design

This will be a single-centre, single-blind, randomized, placebo-controlled, parallel-group, multiple-dose, dose-escalation study.

Each cohort will comprise 8 healthy Caucasian male subjects, 6 of whom will be randomised to receive emodepside, and 2 of whom will be randomised to receive placebo. 3 cohorts will be recruited, to test 3 multiple dose levels of emodepside LSF oral solution over 10 days.

5. Ophthalmological examination will be performed at the second screening visit after all other eligibility criteria have been met, and on Day 10. If deemed necessary by the ophthalmologist, additional ophthalmology follow-up visit(s) may be scheduled for eye-related AEs. Subjects will be given the Ishihara test at screening visit 1.
6. Blood samples taken for glucose and insulin measurement will be used to complete an Oral Glucose Tolerance Test (OGTT). Samples taken will be:
 - on Day -2: at -48, -47, -46 and -44 h before the morning dose on Day 0
 - on Day 1: before and at 1, 2 and 4 h after the morning dose
 - on Day 8: before and at 1, 2 and 4 h after the morning dose
 - On day 120 at 0, 1, 2 and 4 h time points relative to dosingSubjects will fast until completion of the OGTT test; lunch will be provided immediately afterwards
7. Blood samples for measurement of glucose, insulin, glucagon and cortisol will be taken:
 - on Day -1: at -24, -23, -22, -20 and -12 h before the morning dose on Day 0
 - on Day 0: before and at 1, 2, 4 and 12 h after the morning dose
 - on Day 1: before the morning dose
 - on Day 9: before and at the following time points after the morning dose: 1, 2, 4, 12, 24 (Day 10), 48 (Day 11), 72 (Day 12), 96 (Day 13) and 120 h (Day 14); and at follow up (Day 30 (\pm 2 days)). Subjects will fast for the Day 11, 12, 13, 14 and 30 time points.Leptin and prolactin will also be measured at Screening Visit 1 and Day 9, as part of the insulin blood sample.
8. Administration of the study medicine will be done in fasting conditions on Days 0-9 at approximately the same time each morning (\pm 15 mins):
 - in Cohorts 1 & 2, emodepside will be giving in the morning only
 - in Cohort 3, emodepside will be given in the morning and evening (at 12 h intervals). On the last day (day 9), emodepside will be given only in the morning

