- on Day 0: before and at 0.25, 0.5, 1, 1.5, 2, 2.5, 3, 4, 6, 8, 12, and 15 h after the morning dose
 - on Days 1–8: before the morning dose
 - on Day 9: before and at the following times after the morning dose: 0.25, 0.5, 1, 1.5, 2, 2.5, 3, 4, 6, 8, 12, 15, 24, 36 (Day 10), 48 (Day 11), 72 (Day 12), 96 (Day 13) and 120 h (Day 14)
 - at outpatients visits on Days 17, 20, 23 and 27 (± 2 days), and at Follow-up (Day 30 ± 2 days)
- Subjects should rest in the supine position for 10 minutes before blood is drawn (if possible).
13. Blood samples for assay of metabolites of emodepside in plasma will be taken:
- on Day 0: before and at 0.25, 0.5, 1, 1.5, 2, 2.5, 3, 4, 6, 8, 12, and 15 h after the morning dose
 - on Day 9: before and at 0.25, 0.5, 1, 1.5, 2, 2.5, 3, 4, 6, 8, 12, and 15 h after the morning dose
14. Urine for assay of emodepside and its metabolites may be collected at the following time points:
- On Day 0: from 0–4, 4–8, 8–12 and 12–24 h after the morning dose
 - On Day 9: from 0–4, 4–8, 8–12 and 12–24 h after the morning dose
15. Blood and urine samples for clinical laboratory safety tests (haematology, biochemistry, coagulation & urinalysis) will be taken: at Screening Visit 1; on Day -1 (-24 h before the morning dose on Day 0); before the morning dose on Day 0; before the morning dose on Days 1, 5 and 8; before, 24 h (Day 10) and 120 h after the morning dose on Day 9 (Day 14); at the Day 23 outpatient visit (± 2 days); at Follow-up (Day 30 ± 2 days); and at long-term follow-up (Days 60, 90 and 120 ± 2 days).
- Subjects should rest in the supine position for 10 minutes before blood is drawn (if possible).
16. Serology tests will comprise HIV 1 & 2, hepatitis B & C, and HbA1c
17. Blood samples for measurement of leptin and prolactin will be taken at Screening Visit 1 and before the morning dose on Day 9.
18. Subjects will be admitted to the ward on Day 119, before the Day 120 long-term follow-up visit.

7 Planned Analyses

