1.2 AUC Calculations

The AUC will be calculated by a combination of linear and logarithmic methods. The linear trapezoidal method will be employed for all incremental trapezoids arising from increasing concentrations and the logarithmic trapezoidal method will be used for those arising from decreasing concentrations.

AUC_(0-∞) values with <20% of this area extrapolated will be reported.

It is acceptable to include data from profiles with >20% extrapolated as long as at least 80% of the profiles in the study have <20% of the AUC_(0-∞) as extrapolated area. In this instance, individual plasma concentration-time profiles for which the extrapolated areas are >20% of AUC_(0-∞) will be identified.

It is unacceptable to use AUC_(0-∞) data if >40% of the AUC has been extrapolated, except in specific situations which should be carefully justified in the study report.

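### Day 0 Vz/F is defined as a terminal-phase volume but can rest on at most 24 h of data (12 h in Cohort 3) for a drug with a 523 h terminal half-life, so it will come out several-fold too small

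*SAP*

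**What the plan says.** Vz/F is an exploratory Day 0 parameter in SAP 4.2.2 and protocol 2.3. Protocol 8.4.2 and SAP Appendix B 3.1.1 give the formula Dose/(λz × AUC∞), and the SAP defines the result as "Apparent volume of distribution during terminal phase after non-intravenous administration". λz, AUC∞ and the percentage extrapolated are not listed as Day 0 outputs; they appear only in the Day 9 table (Appendix B 3.1.2).

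Plasma samples are taken "on Day 0: before and at 0.25, 0.5, 1, 1.5, 2, 2.5, 3, 4, 6, 8, 12, and 15 h after the morning dose", and then "on Days 1–8: before the morning dose" (SAP, note 12 to the schedule of events). The Day 1 pre-dose sample is therefore the last one before the second dose in Cohorts 1 and 2. Cohort 3 is re-dosed at 12 h (note 8).

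Protocol 1.4 states: "Terminal plasma half-life is 523 h". For the early decline it says: "After 3, 7, 16 and 47 h the maximum plasma concentration is reduced to 50%, 25%, 12.5% and 6.25% respectively". Protocol 1.5 adds a dominant 0–24 h half-life of about 11 h.

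SAP Appendix B 1.2 sets three tiers for AUC∞. It is reported when less than 20% is extrapolated. Profiles above 20% may be included only if at least 80% of profiles are below 20%. It is unacceptable to use "data if >40% of the AUC has been extrapolated" unless this is specifically justified.

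**The concern.** A terminal-phase volume needs the terminal slope and an AUC∞ that contains the terminal area. The Day 0 window is 24/523 = 4.6% of one terminal half-life, or 12/523 = 2.3% in Cohort 3. Any slope fitted there describes distribution. λz is then far too large and AUC∞ far too small. These errors push Vz/F in opposite directions, but the slope error is much the larger, so Vz/F is too small.

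The study report would carry a precise-looking volume under a label it does not meet. Day 9 sampling runs to Day 30, 504 h after the last dose, so Day 9 λz can come much closer to the terminal slope. The same symbol would then stand for two unlike quantities, and a reader could mistake the difference for a change in volume with repeated dosing.

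**Working it through.** **Inputs.** From protocol 1.4: the decay milestones, the 523 h half-life, and a tmax that "for the LSF solution is consistently about 1 h post-dose when fasted". From the SAP: the sampling times, linear-up/log-down AUC, λz from the best adjusted R² with at least three points after Cmax, and AUC∞ using the predicted last concentration. One assumption is needed: the size of the 523 h phase at 47 h. It cannot exceed 6.25% of Cmax, the total level at that time; I ran 1% to 6.25%. The top value is the one kindest to the plan.

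**The protocol's own figure.** A log-linear fit to the last 5 or 6 points up to 24 h gives 9.4 to 12.3 h, depending on whether milestone times count from dose or from tmax. This agrees with the stated 11 h.

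**Reference volume** (Cmax = 1, times from dose, the whole 47 h level terminal):
- 0–1 h: 0.50; 1–3 h: 0.5 × 2/ln 2 = 1.44; 3–7 h: 0.25 × 4/ln 2 = 1.44; 7–16 h: 0.125 × 9/ln 2 = 1.62.
- C24 = 0.125 × 2^(−8/31) = 0.1045. 16–24 h: 0.92; 24–47 h: 1.88.
- Beyond 47 h: 0.0625 × 523/ln 2 = 47.16.
- AUC∞ = 54.96. Reference volume (Dose = 1) = (523/ln 2)/54.96 = 754.5/54.96 = 13.73.

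**Day 0 volume on the same profile, at the SAP's sampling times:**
- 24 h, using the protocol's 11 h half-life: AUC24 = 5.96; extrapolated 0.1045 × 11/ln 2 = 1.66 (21.8% of 7.62). Volume = 15.87/7.62 = 2.08. Ratio 13.73/2.08 = 6.6.
- 24 h, SAP rule (8, 12, 15 and 24 h points): half-life 14.5 h, AUC∞ 8.02, extrapolated 25.7%. Volume = 20.92/8.02 = 2.61. Ratio 5.3. True share beyond 24 h: 1 − 5.96/54.96 = 89%.
- 12 h, SAP rule (6, 8 and 12 h points): half-life 7.6 h, AUC12 4.44, AUC∞ 6.28, extrapolated 29.4%. Volume = 10.96/6.28 = 1.75. Ratio 7.8. True share beyond 12 h: 1 − 4.44/54.96 = 92%.

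**Range** over both readings of the milestone times, terminal amplitudes of 1% to 6.25%, and both log-linear interpolation and a three-exponential curve with the last half-life fixed at 523 h:

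| | 24 h (Cohorts 1–2) | 12 h (Cohort 3) |
|---|---|---|
| Fitted half-life | 13.5–23.5 h | 4.5–7.9 h |
| Apparent extrapolation | 23–38% | 17–30% |
| AUC∞ truly unobserved | 64–89% | 72–92% |
| Vz/F too small by | 5.3- to 17-fold | 8- to 37-fold |

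The 64% comes from a 1% amplitude: 1 − 6.39/17.7. It shifts by a few points with how the non-terminal remainder after 47 h is assumed to decay. Fixing the number of points instead of using the automatic rule gave a lowest ratio of 4.5.

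**The extrapolation check.** With an assumed 10% log-scale error, 31–50% of 24 h profiles and 23–65% of 12 h profiles fell below 20% apparent extrapolation. Most others fell between 20 and 40%, and 0–17% exceeded 40%. The 80%-of-profiles condition was not met in any scenario.

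**Cohort 3 beyond 12 h.** Adding a second identical dose at 12 h, fits to the last 3 to 5 points up to 24 h have a negative λz, which Appendix B 1.3 does not allow. The best adjusted R² from points after Cmax is about 0.15 to 0.17.

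**The case against.** A reader might infer that the Day 0 value passes the SAP's extrapolation check. The documents do not support that. The 40% bar is only the last of three tiers; the computed values mostly lie between 20 and 40%, which fails the first tier, and the 80% condition that would admit them was not met. What stands is narrower: the check sees the wrong percentage, and it is written for AUC∞, not for Vz/F. Since AUC∞ and its extrapolated share are not Day 0 outputs, nothing in the check stops Vz/F being reported.

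A reader might also infer that λz should not be estimated on Day 0 at all. That would do harm. Appendix B 3.1.1 does not calculate AUC12 or AUC24 when the last quantifiable time falls short of the interval and λz is not estimable. Actual sampling times are used, so a last sample slightly before 12 or 24 h is plausible. These are main PK parameters and feed the AUC accumulation ratio.

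On Cohort 3, it would be too strong to say that the automatic rule will use the 15 h and 24 h samples. Appendix B 1.3 leaves room for judgement about which points are terminal. The fair point is that no 12 h cut-off is written and no minimum adjusted R² is set.

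Nor is a Day 0 versus Day 9 comparison of Vz/F planned: accumulation ratios are specified only for AUC and Cmax, and the SAP's Day 9 formula uses the dosing-interval AUC. The risk is misreading, not a planned false contrast. Finally, the sponsor already separates a dominant from a terminal half-life, and Vz/F feeds no escalation or stopping rule. That limits the impact but does not make the Day 0 definition achievable.

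**Conclusion.** Wrong as written, with minor impact. Day 0 cannot supply a terminal-phase volume. Under the SAP's own rules the result is too small by at least about 5-fold in Cohorts 1 and 2, and by about 8-fold in Cohort 3 when the fit stops at 12 h. The direction and the several-fold size held under every assumption tried. The upper ends, 17- and 37-fold, are not firm, because they rest on a terminal amplitude of 1% of Cmax that is assumed. The calculation also takes the preliminary single-dose decay figures and the 523 h half-life in protocol 1.4 at face value.

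**What to change.** 1. Delete Day 0 Vz/F from SAP 4.2.2 and Appendix B 3.1.1 and from protocol 2.3 and 8.4.2. Alternatively, keep it under a label saying that it is not a terminal-phase volume.
2. Keep Day 0 λz only for the short extrapolation of AUC12 or AUC24 when the last quantifiable time falls just short of 12 or 24 h, and do not report it as terminal.
3. State that the Cohort 3 Day 0 fit uses samples up to 12 h only.
4. Compute Day 0 MRTlast with AUC to the last quantifiable time, as protocol 8.4.2 does. Appendix B 3.1.1 currently divides by AUC∞, which carries the same problem.

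The cost is one exploratory parameter and a few lines of text. No sample, main PK parameter or accumulation ratio is lost.
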